### Amendment [a]

#### Overall Rationale for the Amendment:

The protocol is being amended to address FDA recommendations on contraceptive and barrier guidance. This amendment is considered as non-substantial.

Section # and Name	Description of Change	Brief Rationale
10.4.2 Contraception Guidance	Revised to include 2 forms of effective methods of contraception where at least 1 form must be a highly effective method of contraception.	Based on FDA feedback
	Deleted “total abstinence” from the list of highly effective contraception.	Based on FDA feedback

## 1. Protocol Summary

### 1.1. Synopsis

**Protocol Title:** A Bioequivalence Study to Compare the Pharmacokinetics of Tirzepatide Administered Subcutaneously by a Fixed-Dose Multi-use Prefilled Pen Versus Single-Dose Pen in Healthy Participants

**Brief Title:** Bioequivalence Study to Compare the PK of Tirzepatide Administered by Fixed-Dose Multi-use Prefilled Pen Versus Single-Dose Pen in Healthy Participants

**Regulatory Agency Identifier Number(s):** IND128801

#### Rationale:

Study I8F-MC-GPIP (GPIP) will assess the pharmacokinetics (PK), safety, and tolerability of a 5-mg subcutaneous (SC) dose of tirzepatide solution formulation administered via fixed-dose multi-use prefilled pen (MUPFP) (test) versus a single-dose pen (SDP) (reference). The SDP autoinjector device is the currently approved commercial single-dose, single-use pen presentation of tirzepatide, while the MUPFP is being developed as an alternative multi-dose option. This study will provide PK bioequivalence data for tirzepatide when it is administered via the MUPFP versus the SDP device.

#### Objectives and Endpoints

Objectives	Endpoints
Primary	

 
To evaluate the bioequivalence between the MUPFP (test) and the SDP (reference), as assessed using tirzepatide PK in healthy participants
 
	
 
<math>C_{max}</math>, <math>AUC_{(0-t)}</math>, and <math>AUC_{(0-\infty)}</math>
 

Secondary	
 
<math>t_{max}</math>
 
Incidence of AEs
 

Abbreviations: AE = adverse event;  $AUC_{(0-t)}$  = area under the concentration versus time curve from time zero to time  $t$ ;  $AUC_{(0-\infty)}$  = area under the concentration versus time curve from zero to infinity;  $C_{max}$  = maximum observed drug concentration; MUPFP = multi-use prefilled pen; PK = pharmacokinetics; SDP = single-dose pen;  $t_{max}$  = time of maximum observed drug concentration.

**Brief Summary of Study Design:**

Study GPIP is a multicenter, open-label, randomized, 2-period, 2-sequence, crossover study conducted in healthy participants.

**Study Population:**

Healthy participants.

**Number of Participants:**

Approximately 65 participants will be enrolled so that at least 54 participants complete the study.

**Intervention and Planned Duration for an Individual Participant:**

The study involves a comparison of:

- a single dose of 5 mg tirzepatide administered SC via MUPFP
- a single dose of 5 mg tirzepatide administered SC via SDP

The study duration for individual participants, inclusive of screening is expected to be approximately 14 weeks, divided as follows:

- Screening: up to 27 days prior to Day -1
- Treatment Periods 1 and 2: Day 1 to Day 36, including single dosing with tirzepatide on Day 1 of each period
- Washout: there will be a washout of at least 35 days between tirzepatide dose administrations
- Follow-up: Period 2, Day 36 ( $\pm 1$ ) will be considered as the final follow-up visit

[figure not shown]
**Ethical Considerations of Benefit/Risk:**

As of 26 September 2022, tirzepatide (MOUNJARO™) was approved in the US, EU, and Japan as an adjunct to diet and exercise to improve glycemic control in adults with type 2 diabetes mellitus. Risks of tirzepatide have been consistent with risks associated with other glucagon-like peptide (GLP)-1 receptor agonists that are currently marketed. Potential risks include, but are not limited to, gastrointestinal effects, acute pancreatitis, increases in heart rate, and hypoglycemic events (GLP-1 receptor agonist class effect), which are all monitorable.

There is no anticipated therapeutic benefit in healthy participants.

**Data Monitoring Committee: No**

## 1.2. Schema

Abbreviations: CRU = clinical research unit; PK = pharmacokinetics; PFP = prefilled pen, SDP =single dose pen

### 1.3. Schedule of Activities (SoA)

	Screening	Periods 1 and 2 Study Days – at least 35 days washout between Day 1 doses												ED b	Comments
Procedure	D -28 to D -2	D -1 a	D1 a	D2	D3	D4	D5	D6	D7	D8	D15	D21	D36 (±1) a		
Informed consent	X														
Participant admission to CRU		X													
Ethanol and urine drug screen testing	X	X													Per site CRU local requirements
Tirzepatide dosing			0 hour												Study drug will be administered after an overnight fast of at least 8 hours.
Participant discharge from CRU						X									Inpatient stay may be extended at the investigator's discretion for safety monitoring.
Outpatient visit							X	X	X	X	X	X	X		
Medical history and demographics	X														
Physical examination /medical assessment	X		Predose			X							X	X	Full physical examination at screening. Thereafter, assessments performed to include medical review and targeted, symptom-driven examination, as appropriate. Additional assessments may be performed at investigator's clinical discretion.
Weight	X		Predose										X	X	
Height	X														
Temperature	X		Predose												
Safety 12-lead ECG c	X				X									X	
Vital signs (hours)	X		Predose, 12	24	48	72				X	X	X	X	X	Additional unscheduled measures may be taken, at the clinical discretion of the investigator.
Clinical laboratory tests	X		Predose							X			X	X	See Appendix 2 for details. Day 1 predose sample is for baseline only and need not be reviewed prior to first dosing. Performed by local laboratory at screening and central laboratory for subsequent visits.
Pregnancy test	X		Predose										X	X	Female participants only. Serum pregnancy test will be performed at screening and urine pregnancy tests at subsequent visits.
FSH test, if applicable	X														Female participants considered to be postmenopausal only. Women with confirmed nonchildbearing potential status can be exempted from further pregnancy tests during the study after screening.
AEs/concomitant medications	X	X	X	X	X	X	X	X	X	X	X	X	X	X	

	Screening	Periods 1 and 2 Study Days – at least 35 days washout between Day 1 doses												ED b	Comments
Procedure	D -28 to D -2	D -1 a	D1 a	D2	D3	D4	D5	D6	D7	D8	D15	D21	D36 (±1) a		
Pharmacogenetic sample c			Predose												Single sample in Period 1 only.
Blood glucose monitoring (hours) c			Predose, 12	24, 36	48	72									Performed using a bedside glucose monitor. Additional unscheduled measurements may be taken at the clinical discretion of the investigator.
PK sampling (hours) c			Predose, 8, 12	24, 36	48	72	96	120	144	168	336	480	X	X	

Abbreviations: AE = adverse event; CRU = clinical research unit; D or d = day; ECG = electrocardiogram; ED = early discontinuation; FSH = follicle-stimulating hormone; PK = pharmacokinetic(s).

a Period 2, Day -1 procedures (pregnancy tests) and some Period 2, predose procedures (physical examinations, medical assessments, ethanol and drug screening and clinical laboratory assessments) may be omitted if Period 1, D36 (±1) procedure dates occur within 4 days of Period 2 dosing. Period 2, Day 36 (±1) will also be considered as the final follow-up visit.

b Within 14 days upon confirmation of early discontinuation.

c Predose sample should be collected approximately 2 h prior to dose administration.

Note: All sampling and procedure times are given relative to dosing (Time 0 hour) with tirzepatide (predose or hours postdose). Unless otherwise indicated, predose procedure may be performed any time prior to dosing.

If multiple procedures take place at the same time point, the following order of the procedures should be used: ECGs, vital signs, PK sample (record of actual PK sampling time is the priority), clinical laboratory sample, blood glucose and pharmacogenetic sample.

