### **8.2.9. Pregnancy Testing**

Pregnancy testing will be performed for all female participants at the time points detailed in the SoA (Section 1.3). Serum pregnancy testing will be used at screening. Urine pregnancy testing will be used at all other time points, as per SoA. See Section 8.3.2 for more detail.

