## Safety Laboratory Tests

Hematology a	Clinical Chemistry a
Hematocrit	Sodium
Hemoglobin	Potassium
Erythrocyte count (RBC)	Bicarbonate
Mean cell volume	Chloride
Mean cell hemoglobin	Calcium
Mean cell hemoglobin concentration	Glucose (fasting)
Leukocytes (WBC)	Blood urea
Absolute counts of:	Total protein
Neutrophils	Albumin
Lymphocytes	Total bilirubin
Monocytes	Alkaline phosphatase
Eosinophils	Aspartate aminotransferase
Basophils	Alanine aminotransferase
Platelets	Creatinine
	Amylase
	Lipase
Urinalysis a	
Specific gravity	Hepatitis B surface antigen b
pH	Hepatitis C antibody b
Protein	HIV or HIV antibody b
Glucose	FSH c
Ketones	Pregnancy test d
Bilirubin	Ethanol and urine drug screen testing e
Urobilinogen	
Blood	
Nitrite	
Leukocytes (WBC)	
Microscopic examination of sediment f	

Abbreviations: FSH = follicle-stimulating hormone; HIV = human immunodeficiency virus; RBC = red blood cell; WBC = white blood cell.

- a Performed by central laboratory except at screening which may be performed by a local laboratory. Results will be validated by the laboratory at the time of initial testing.
- b Performed by local laboratory at screening only.
- c FSH - Performed at screening only for females to confirm postmenopausal status.
- d Pregnancy test - Serum pregnancy test will be performed at screening and urine pregnancy tests at subsequent visits. Women with confirmed nonchildbearing potential status can be exempted from further pregnancy tests during the study after screening.
- e Performed locally at site during screening and admission on Day -1. Additional testing may be performed at the discretion of the investigator if warranted.
- f Test only if dipstick result is abnormal (ie, positive for blood, protein, or nitrites)

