### 10.4.2. Contraception Guidance

#### Contraception guidance for females

WOCBP and women not of childbearing potential may participate in this trial.

WOCBP who are completely abstinent as their preferred and usual lifestyle, or in a same-sex relationship as their preferred and usual lifestyle:

Must...	Must not...
agree to either remain abstinent or stay in a same-sex relationship without sexual relationships with males	
 
use periodic abstinence methods 
 
calendar
 
ovulation
 
symptothermal, or
 
post-ovulation
 
 
 
declare abstinence just for the duration of a trial, or
 
use the withdrawal method
 

WOCBPs who are NOT completely abstinent as their preferred and usual lifestyle, or NOT in a same-sex relationship as their preferred and usual lifestyle, must do the following:

Topic	Condition
Pregnancy testing	Have a negative serum test result at screening followed by a negative urine result within 24 hours prior to treatment exposure. See the protocol SoA for subsequent pregnancy testing requirements.
Contraception	Agree to use 2 forms of effective methods of contraception where at least 1 form must be a highly effective method of contraception. These forms of contraception must be used for the duration of the study.

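### Does SoA footnote a go wrong by letting sites skip the Period 2 ethanol/drug screen when no such screen is scheduled at Day 36?

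*Protocol*

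**What the plan says.** Footnote a to the SoA (Protocol 1.3) covers two groups of assessments: "Period 2, Day -1 procedures (pregnancy tests) and some Period 2, predose procedures". The second group is physical examinations, medical assessments, the ethanol and drug screen, and clinical laboratory work. The condition for leaving them out is the closeness of the Period 1 Day 36 visit: "drug screening and clinical laboratory assessments) may be omitted if Period 1, D36 (±1) procedure dates occur within 4 days of Period 2 dosing".

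The SoA row "Ethanol and urine drug screen testing" is marked at screening and Day -1 only, with the comment "Per site CRU local requirements". Footnote e of the safety laboratory table in Appendix 2 (Protocol 10.2) agrees: "Performed locally at site during screening and admission on Day -1. Additional testing may be performed at the discretion of the investigator if warranted".

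The pregnancy-test row is marked at screening, Day 1 predose, Day 36 and early discontinuation. A general note under the SoA adds: "Unless otherwise indicated, predose procedure may be performed any time prior to dosing". Protocol 10.4.2 asks certain women of childbearing potential for a negative serum test at screening, "followed by a negative urine result within 24 hours prior to treatment exposure. See the protocol SoA for subsequent pregnancy testing requirements". Protocol 8.2.9 also sends the timing of pregnancy tests to the SoA.

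**The concern.** A waiver tied to a recent visit normally works because that visit produced the result being waived. For the ethanol/drug screen, Day 36 produces no scheduled result, so the stated condition has nothing to refer to. A site that applies the footnote could give the second dose with no scheduled screen since Period 1 Day -1.

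The day labels add to the doubt. The footnote places the pregnancy test at Day -1 and the screen at predose, and the grid has them the other way round. A reader could ask whether the single scheduled pre-dose pregnancy test of Period 2 may be skipped, and how that fits with the 24-hour wording in 10.4.2.

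At stake would be uniform testing before re-dosing in a multicenter study.

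**Working it through.** The plan states no figure on this point, so there is none to reproduce. The check has two parts.

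**1. Footnote a against the SoA grid**

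| Item named in footnote a | Footnote label | Position in the grid before dosing | Marked at Day 36? |
|---|---|---|---|
| Pregnancy test | Day -1 | Day 1 predose | Yes |
| Ethanol/drug screen | Predose | Day -1 | No |
| Physical examination | Predose | Day 1 predose | Yes |
| Medical assessment | Predose | Day 1 predose | Yes |
| Clinical laboratory tests | Predose | Day 1 predose | Yes |

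Physical examination and medical assessment share one SoA row, so the five items come from four rows. Three of the five labels agree with the grid and two are swapped. One item has no Day 36 counterpart.

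**2. Age of the last scheduled result at the Period 2 dose**

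Inputs: washout of at least 35 days between doses (Protocol 4.1.3); Day 36 visit window of ±1 day and waiver limit of 4 days (SoA). Count Period 1 Day 1 as day 1 and Period 1 Day -1 as the calendar day before it, day 0. Read the waiver limit as 0 to 4 calendar days from visit to dose.

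- Earliest Period 2 dose: 1 + 35 = day 36.
- Latest Period 1 Day 36 visit: 36 + 1 = day 37.
- Latest Period 2 dose under the waiver: 37 + 4 = day 41.
- Age of the Period 1 Day -1 screen: 36 − 0 = 36 days at least, 41 − 0 = 41 days at most.
- Age of results in the three rows marked at Day 36: 0 to 4 days, by the waiver condition itself.
- Age of a Period 2 Day -1 screen, if done as the grid shows: 1 day.

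**What depends on the screen**

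- Drug-screen positivity is an exclusion criterion (Protocol 5.2, criterion 18). Protocol 5 applies the criteria at screening and not continuously, unless a criterion says otherwise.
- Protocol 7.1 and 7.2 do not list a Period 2 screen result as a reason to withhold the dose or withdraw the participant. They leave general discretion to the investigator.
- The primary analysis (Protocol 9.3.2; SAP 4.3) uses tirzepatide concentrations and a model with treatment, sequence, period and subject. Neither the screen nor its date enters the model or the sample size calculation.

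**The case for a change.** The strongest case for a change is that the waiver will be used often. With the minimum washout, the second dose falls on Period 1 Day 36 itself, which meets the condition. The stated study duration fits that timetable: 28 days of screening + 35 days between doses + 35 days to Period 2 Day 36 = 98 days, or 14 weeks. Protocol 8 treats keeping to the SoA as essential, and the repair would cost one footnote. A restriction on alcohol before admission (Protocol 5.3.2) is not a test, and discretionary testing does not create a scheduled one.

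All of that stands as a description of the text. It does not show harm:

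- The footnote names the screen expressly. A footnote that grants a specific exception to a grid is ordinary drafting, and it never says that a Day 36 result takes the place of the omitted test. That is an inference from the timing condition.
- Variation between sites is already accepted for this row through its comment on local requirements, so one uniform rule was not the protocol's aim here.
- The label swap has little practical effect. Since predose work may be done at any time before dosing, a predose pregnancy test can be done on Day -1, and a Day -1 screen is also before dosing.
- The grid has one pregnancy test before dosing in each period. The waiver can only sensibly refer to that test, and a Day 36 pregnancy test exists.
- A definite clash with the 24-hour wording cannot be claimed. That wording may concern first exposure only, because 10.4.2 itself sends later testing to the SoA.
- Investigators may add tests (Appendix 2), and Protocol 5.3 allows compliance to be reviewed before a participant continues.

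**Conclusion.** This is a clerical slip and no change to the plan follows. The facts hold: one of the five items in footnote a has no Day 36 counterpart, two of its five day labels are swapped against the grid, and under the waiver the last scheduled ethanol/drug result would be 36 to 41 days old at the second dose. These ages rest on counting calendar days and on the Period 1 Day -1 screen being the last one done. How many participants would be affected cannot be stated, because the documents give about 65 enrolled and at least 54 completing but not the number who reach Period 2 under the waiver.

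The consequence is not shown. No stated dosing condition is breached, the protocol leaves this test to local practice, and the bioequivalence estimates, confidence intervals and power do not depend on it. Footnote a, the SoA rows, Appendix 2 footnote e and section 10.4.2 do need to be reconciled in wording. That is housekeeping, and which testing rule applies is for the sponsor to decide. It would not alter the design, the analysis or the conclusions.

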## 2. Introduction

### 2.1. Study Rationale

As of 26 September 2022, tirzepatide (MOUNJARO™) received regulatory approval in the US, EU, and Japan. Tirzepatide is indicated as an adjunct to diet and exercise to improve glycemic control in adults with T2DM. In addition, it is being developed as a therapy for the indications of chronic weight management, nonalcoholic steatohepatitis, obstructive sleep apnea, and heart failure with preserved ejection fraction. It is administered QW through SC injection.

Study I8F-MC-GPIP (GPIP) will assess the PK, safety, and tolerability of a 5-mg SC dose of tirzepatide solution formulation administered using the MUPFP (test) versus the SDP (reference).

The SDP is the currently approved commercial presentation of tirzepatide. The fixed-dose MUPFP is being developed as an alternative option for future commercialization.

### 2.2. Background

Tirzepatide (LY3298176) is a GIP and GLP-1 RA. It is a 39 amino acid synthetic peptide with agonist activity at both the GIP and GLP-1 receptors. Its structure is based on the GIP sequence and includes a C20 fatty di-acid moiety that prolongs the duration of action. It is administered QW through SC injection in a SDP.

Tirzepatide has a chemical structure and pharmacologic profile, ie, distinct from GLP-1 RAs due to the additional effects on GIP receptor, which is unique compared to the marketed incretin mimetics. As an agonist, tirzepatide combines the signaling of each receptor for improved glycemic control (Coskun et al. 2018). By virtue of being an agonist incretin mimetic, tirzepatide has the potential for reaching higher efficacy in target tissues such as the insulin-producing pancreatic  $\beta$  cells that express both GIP and GLP-1 receptors before reaching its therapeutic limitation, which supports its use as a treatment for T2DM.

A solution formulation of tirzepatide for injection in a SDP was developed for QW SC administration. This drug product formulation is composed of tirzepatide drug substance, sodium phosphate, sodium chloride, and water for injections.

The current commercial configuration is a single integral product with 0.5-mL sterile drug product solution contained in a 1-mL glass syringe with a plunger, which is assembled into a PFP (or autoinjector). The finished form is a SDP with a spring-driven design to administer the 0.5 mL. The 6 available strengths are 2.5, 5, 7.5, 10, 12.5, and 15 mg.

The MUPFP is configured to deliver multiple 0.6-mL doses of a single strength. The MUPFP uses a 3-mL cartridge that is preassembled into the device and is not replaceable. Six separate MUPFPs, 1 for each dose strength, are planned to match the approved SDP offering (2.5, 5, 7.5, 10, 12.5, and 15 mg). Each MUPFP will contain sufficient volume to deliver 4 doses covering 1 month of therapy.

### **2.3. Benefit/Risk Assessment**

As of 26 September 2022, tirzepatide (MOUNJARO) was approved in the US, EU, and Japan as an adjunct to diet and exercise to improve glycemic control in adults with T2DM. Risks of tirzepatide have been consistent with risks associated with other GLP-1 RAs that are currently marketed. Potential risks include, but are not limited to, GI effects, acute pancreatitis, increases in heart rate, and hypoglycemic events (GLP-1 RA class effect), which are all monitorable.

No clinically significant safety or tolerability concerns have been identified during clinical investigation of tirzepatide up to the highest single dose level of 8 mg or multiple weekly doses up to 15 mg, attained by stepwise dose escalation. The maximum tolerated dose as a single dose of tirzepatide in healthy participants was determined to be 5 mg. Based on this information, the 2x single 5-mg doses to be administered in Study GPIP are reasonably anticipated to be tolerable in this group of healthy participants.

There is no anticipated therapeutic benefit in these healthy participants.

More information about the known and expected benefits, risks, SAEs, and reasonably anticipated AEs of tirzepatide are to be found in the package insert of tirzepatide.

### 3. Objectives and Endpoints

Objectives	Endpoints
Primary	

 
To evaluate the bioequivalence between the MUPFP (test) and the SDP (reference), as assessed using tirzepatide PK in healthy participants
 
	
 
<math>C_{max}</math>, <math>AUC_{(0-t)}</math>, <math>AUC_{(0-\infty)}</math>
 

Secondary	

 
To evaluate the additional PK parameter
 
To evaluate the safety and tolerability of a single subcutaneous dose of tirzepatide administered through MUPFP (test) versus SDP (reference)
 
	
 
<math>t_{max}</math>
 
Incidence of AEs
 

Abbreviations: AE = adverse event;  $AUC_{(0-t)}$  = area under the concentration versus time curve from time zero to time  $t$ ;  $AUC_{(0-\infty)}$  = area under the concentration versus time curve from zero to infinity;  $C_{max}$  = maximum observed drug concentration; MUPFP = multi-use prefilled pen; PK = pharmacokinetics; SDP = single-dose pen;  $t_{max}$  = time of maximum observed drug concentration.

## 4. Study Design

### 4.1. Overall Design

This is a multicenter, open-label, randomized, 2-period, 2-sequence, crossover study conducted in healthy participants.

The study will include 2 treatment arms. Approximately 65 participants may be enrolled so that at least 54 participants complete the study. Participants will be randomly assigned 1:1 to the 2 treatment sequences. It is intended that approximately the same number of participants will be randomly assigned into each treatment sequence. The treatment sequence are:

- a single dose of 5 mg tirzepatide administered SC via MUPFP followed by SDP; or
- a single dose of 5 mg tirzepatide administered SC via SDP followed by MUPFP.

The study duration for individual participants, inclusive of screening, is expected to be approximately 14 weeks.

